5. HANDLING OF SERIOUS ADVERSE EVENTS

Patients developing serious or life-threatening adverse events will have the study drug stopped, the adverse event appropriately treated, and an adverse event form completed. The investigators must notify the Ethical Review Committee on the event within 24 hours of its occurrence.

6. RATIONALE

In this study we propose to compare the efficacy of a single 20 mg/kg (maximum 1.0 g) oral dose of azithromycin oral suspension with 12.5 mg/kg (maximum individual dose of 500 mg) 6 hourly dose of erythromycin oral suspension administered for 3 days (12 doses) in the treatment of children with cholera due to *V. cholerae* O1 or *V. cholerae* O139. If azithromycin is found effective in this study, it will be the first single dose therapy demonstrated to be effective in children. Thus, the findings of this study may have important implications for treatment of endemic cholera, and more importantly in the management and control of large epidemics, particularly when the infections are caused by strains of *V. cholerae* O1 and O139 resistant to conventional drugs used in children- trimethoprim-sulfamethoxazole and furazolidone.

7. DEFINITIONS

- 7.1 **Clinical success:** Cessation of watery stool within 96 hours of administration of the study drug without relapse
- 7.2 **Clinical failure:** Continuation of watery stool for > 96 hours
- 7.3 **Clinical relapse:** Cessation of watery stool within 96 hours of administration of the study drugs, its absence for 24 hours or more, and its recurrence anytime during study or between discharge and follow up 7 days from the time of discharge.
- 7.4 **Bacteriological success:** Eradication of the infecting *V. cholerae* organism from fecal specimens within 48 hours of initiation of study drugs without its subsequent isolation
- 7.5 **Bacteriological failure:** Isolation on study day 3 or thereafter from fecal samples of the study patients the same biotype and serotype of *V. cholerae* as was isolated on admission.
- 7.6 **Bacteriological relapse:** Failure to isolate the infecting *V. cholerae* from stool specimen on two consecutive study days, followed by its isolation any time after this, including at the follow-up visit.
- 7.7 **Reinfection:** Isolation of a different biotype or serotype of *V. cholerae* as was isolated on admission, or of the same biotype and serotype with a different antimicrobial susceptibility pattern.
- 7.8 **Duration of diarrhea:** The interval between administration of study drugs to the end of the last 6-hour period the patient had a watery stool.

Facilities Available

Describe the availability of physical facilities at the place where the study will be carried out. For clinical and laboratory-based studies, indicate the provision of hospital and other types of patient's care facilities and adequate laboratory support. Point out the laboratory facilities and major equipments that will be required for the study. For field studies, describe the field area including its size, population, and means of communications. (TYPE WITHIN THE PROVIDED SPACE).

Site: The Research Ward of the Dhaka Hospital of ICDDR,B will be used for hospitalization of the study children. This facility is being used for similar clinical trials for decades.

Study population: The Dhaka Hospital provides treatment to over 110,000 diarrheal patients each year, about 70% of whom are children <15 years of age. Cholera is endemic in Bangladesh, and thousands of children with cholera are treated at this hospital each year; study children will be selected from among them.

Laboratory facilities: The clinical laboratory services of the Laboratory Sciences Division of ICDDR,B will be used for all study related laboratory investigations (tests). These laboratories are regularly used for all protocols of the Centre.

Equipments: No equipment other than those required for routine clinical examination of children will be required for this study.

Data Analysis

Describe plans for data analysis. Indicate whether data will be analyzed by the investigators themselves or by other professionals. Specify what statistical softwares packages will be used and if the study is blinded, when the code will be opened. For clinical trials, indicate if interim data analysis will be required to monitor further progress of the study. (TYPE WITHIN THE PROVIDED SPACE).

1. Comparability of study groups

1.1 Before administration of the study drug: Age, dehydrated body weight, degree of dehydration, diarrhoea duration, vomiting frequency, and stool output during the rehydration and observation periods as well as other admission characteristics will be compared between the groups.

1.2 Comparison of primary outcome measures: Rates of clinical and bacteriologic success in the two treatment groups will be compared.

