Patients eligible for study will be male (1-15 years of age) or female (5-15 years of age), who have watery diarrhea of ≤ 24 hours and signs of severe dehydration (WHO guidelines), and who have cholera vibrios identified on dark-field microscopic screening of stools. Only those patients who have ≥ 20 ml/kg body weight of stool during a 4 hour observation period following initial rehydration period will be entered into the study; only patients from whom *V. cholerae* O1 or O139 is isolated, and who stay in-hospital for three or more days will be eligible for analysis. Written informed consent will be required from the parents/guardians of all children for their inclusion in the study. Patients will be asked to remain in hospital for full five days from the initiation of drug therapy, and to return for a follow-up visit ten days after discharge. Cultures of stool will be obtained on admission to the study, and daily during hospitalization. Stool will be collected, and the volume of watery stool measured for every six hour period of the study. Major outcomes to be compared in the two treatment groups will be clinical success of therapy, defined as resolution of diarrhoea within 96 hours of initiation of study drugs, and bacteriologic success of therapy, defined as the inability to isolate the infecting strain of *Vibrio cholerae* O1 or O139 after 48 hours of therapy. Other outcomes measures examined will be the incidence of adverse reactions to drugs in the two treatment groups, the duration of watery diarrhea and positive stool cultures, and the total volume of watery/liquid stools during study.

Azithromycin is active against multiply-resistant strains of *V. cholerae* O1 or O139, it is safe for use in children, and it is widely available. If single-dose of azithromycin is found to be effective in the treatment of cholera in this study, it will be a considerable advance in treatment of cholera in children; effective single-dose therapy of childhood cholera has not been previously identified with any drug.

Principal Investigator: Last, first, middle: [name]

KEY PERSONNEL (List names of all investigators including PI and their respective specialties)

Name	Professional Discipline/ Specialty	Role in the Project
1. [name]	Internal Medicine	Principal investigator
2. [name]	Internal Medicine	Co-investigator
3. [name]	Pediatrics and Infectious Diseases	Co-investigator
4. [name]	Biochemistry	Research Officer

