3.5 Treatment regimen and randomization

After informed consent has been obtained, patients will be randomly assigned in equal numbers to receive either a single 20 mg/kg (maximum 1.0 g) dose of azithromycin oral suspension, or 12.5 mg/kg (maximum individual dose of 500 mg) of erythromycin oral suspension every 6 hours for 3 days (12 doses). Upon final enrollment in the study, patients will be assigned consecutive study numbers which will have been randomly pre-assigned to one of the two treatment regimen using a computer generated set of random numbers and a block randomization method using a fixed block length of 4.

The time of administration of drug will be considered as the beginning of the study, and each consecutive 24-hour period from this time will constitute a study day. For patients who vomit within 10 minutes of ingestion of the study drug, the dose will be repeated and the event will be recorded; incidence of repeat dosing will be compared between the two study groups at the time of analysis.

A double dummy technique will be used in order to blind treatment regimen; study drugs will be made available in two colour coded bottles "A" and "B" for each study children. For children in the azithromycin treatment group, bottle "A" will contain active drug and bottle "B" will contain a placebo for erythromycin. For children in the erythromycin treatment group, bottle "A" will contain placebo for azithromycin and bottle "B" will contain active erythromycin. For all study patients, the first dose of study medication will be dispensed from both of the bottles "A" and "B" and the remainder of the doses will be dispensed from bottle "B". Active and placebo for azithromycin and erythromycin will be identical in

appearance, and their concentration will be adjusted to allow dispensing drug as ml/kg of body weight basis (identical in volume/kg). Random numbers will be generated by Pfizer, USA, who will also provide coded drugs for this study.

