3.7 Clinical evaluation and laboratory studies

Study patients will be hospitalized for full five days beginning from the time of initiation of study drug therapy. The following clinical and laboratory evaluations will be performed on the study patients at various time period of the study:

- **Weighting:** Before rehydration, after rehydration, just before initiation of the study drug (after the 4-hour observation period), every 24 hours during hospitalization, and at follow-up.
- **History and physical examination:** Before rehydration, after rehydration, at the time of initiation of study drug therapy, daily during hospitalization, and at follow up. In addition to evaluation of hydration status, the history and physical examinations will also focus on adverse events including vomiting, gastrointestinal distress, and rash.
- **Vital signs:** Rectal or oral temperature, pulse and respiratory rates, and blood pressure will be recorded before rehydration, after rehydration, just before administration of study drug, and then every 6 hours during hospitalization.
- **Quantitation of stool volume and/or weight:** This will be done for the rehydration and the observation periods, and for each 6 hour period of hospitalization.

- **Stool character:** Stool will be characterized as follows:
 - Watery:** Stool that can be poured like water
 - Soft:** Stool that cannot be poured, but that takes the shape of the container.
 - Formed:** Stool that retains its shape.
- **Stool culture for *V. cholerae* O1, O139 and non-O1; and *Shigella* and *Salmonella*:** Will be done before initiation of drug therapy on the day of admission, on study day 3, and at follow up 7 days after discharge from the hospital.
- **Rectal swab culture for *V. cholerae*:** Will be done before initiation of the study drug on the day of admission, and daily during hospitalization.
- **Hematologic studies:** Serum electrolytes, creatinine, hematocrit, and serum Sp.gr. will be measured before and after rehydration, and at 24 hours from the time of initiation of study drug therapy. Complete blood count and platelet count will be performed only once, after initial rehydration, however, may also be done at other time(s) if clinically indicated. A total of 2.5 ml + 3.0 ml + 2.5 ml of venous blood will be collected at above specified times.

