4.1 Primary outcome measures

- Rates of clinical success
- Rates of bacteriologic success

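### Bacteriological success is not tied to the scheduled cultures or to a closed window, so evaluable children are judged on one to four culture occasions after 48 hours, and a culture not taken cannot count against success

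*Protocol*

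**What the plan says.** - **Status of the outcome.** Section 4.1 lists "Rates of bacteriologic success" as a primary outcome, next to clinical success.
- **Success (7.4).** The infecting organism must be eradicated "from fecal specimens within 48 hours of initiation of study drugs without its subsequent isolation". The project summary has a shorter version: the strain cannot be isolated "after 48 hours of therapy". Neither names an end point.
- **Failure (7.5).** This requires a positive finding: "Isolation on study day 3 or thereafter from fecal samples of the study patients" of the biotype and serotype found on admission.
- **Who is analysed.** The project summary restricts analysis to culture-confirmed children "who stay in-hospital for three or more days will be eligible for analysis". It asks children to come back for follow-up but does not make attendance a condition of analysis.
- **Planned observation.** Section 3.7 states: "Study patients will be hospitalized for full five days beginning from the time of initiation of study drug therapy". It schedules a rectal swab on each hospital day, and a stool culture on study day 3 and at follow-up.
- **Study day.** Under section 3.5, "each consecutive 24-hour period from this time will constitute a study day", counted from drug administration. Day 3 is therefore 48 to 72 hours.
- **Follow-up date.** It is 7 days after discharge in sections 3.7 and 7.3, but ten days after discharge in the project summary.

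**The concern.** The schedule in 3.7, the definitions in 7.4 and 7.5, and the evaluability rule in the summary do not connect. Success is the absence of a later isolate, and the number of chances to find one depends on how long the child stays and whether the child returns. Fewer cultures can never raise a child's chance of being called a failure.

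Two things are at stake. If early departure or missed follow-up differs between arms, the comparison of a primary outcome is biased toward the arm observed less. If they are equal, both success rates are inflated and a true difference in late shedding shrinks. That second effect matters because the hypothesis is that one dose of azithromycin is as effective as twelve doses of erythromycin. The protocol's own background reports slower bacterial eradication with single-dose tetracycline and doxycycline than with multiple doses, so the later cultures are where a single-dose arm could plausibly differ.

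Loss of later cultures is realistic. Active dosing ends on day 3, two days before planned discharge, and the staffing justification provides attendants to fetch children who do not return.

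**Working it through.** **No planned figure to reproduce.** The sample size (58 per arm, margin 0.10) rests on clinical success. Its formula gives 2 × 0.95 × 0.05 × (1.645 + 0.842)² / 0.10² = 58.7, which agrees with the stated 58 to within rounding. The protocol gives no expected rate for bacteriological success, so what follows is a count plus illustrations on stated assumptions.

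**Step 1. Culture occasions after 48 hours (sections 3.5 and 3.7, project summary)**

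| Attendance of an evaluable child | Occasions | Number |
|---|---|---|
| Five days and follow-up | days 3, 4, 5, follow-up | 4 |
| Five days, no follow-up | days 3, 4, 5 | 3 |
| Leaves after three completed days, attends follow-up | day 3, follow-up | 2 |
| Leaves after three completed days, no follow-up | day 3 | 1 |

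Day 3 has both a stool culture and a rectal swab. The count is of occasions, not specimens.

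**Step 2. Differential loss.** Assume that a child negative on day 3 has an independent chance r of a positive result at each later occasion (5%, range 2 to 10%), and that the arms differ by 15 percentage points in the share losing k later occasions. The spurious difference is 0.15 × [1 − (1 − r)^k].

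| r | k = 3 (leaves early, no follow-up) | k = 2 (leaves early, attends follow-up) | k = 1 (misses follow-up only) |
|---|---|---|---|
| 2% | 0.15 × 5.9% = 0.9 points | 0.15 × 4.0% = 0.6 | 0.15 × 2% = 0.3 |
| 5% | 0.15 × 14.3% = 2.1 points | 0.15 × 9.75% = 1.5 | 0.15 × 5% = 0.75 |
| 10% | 0.15 × 27.1% = 4.1 points | 0.15 × 19% = 2.85 | 0.15 × 10% = 1.5 |

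These apply to children negative on day 3. Multiplying by the proportion negative on day 3 makes them smaller, so each is a ceiling under its assumptions. In children, 2.1 points is 0.021 × 58 = 1.2 per arm.

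**Step 3. Equal loss.** If a share f of each arm has no later occasion, and leaving is unrelated to shedding, a true difference in late isolation is multiplied by (1 − f). Take r = 5% in one arm and 10% in the other. The difference over three later occasions is 27.1% − 14.3% = 12.8 points. With f = 15% in both arms it appears as 0.85 × 12.8 = 10.9 points.

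**Step 4. A second model.** Let a share π still shed after 48 hours, each occasion detecting a shedder with probability q, independently. Apparent success on k occasions is 1 − π[1 − (1 − q)^k].

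- π = 10%, q = 0.2: 94.1% on four occasions, 98.0% on day 3 alone, a gap of 3.9 points.
- π = 30%, q = 0.3: 77.2% on four, 91.0% on day 3 alone, a gap of 13.8 points.

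Over π = 10 to 30% and q = 0.2 to 0.5 the gap is about 4 to 14 points. If 10 to 30% of one arm had only the day-3 occasion and all other children had four, that arm's rate would rise by about 0.4 to 4 points.

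**Step 5. What missing-as-non-success would do.** Restrict the window to days 3 to 5, so that an early leaver lacks two occasions. At r = 5%, a 15-point imbalance in early leaving would lower the rate in the arm with more leavers by 0.15 × 0.95² = 13.5 points among children negative on day 3. Default scoring as success would raise it by 1.5 points. The cure can bias the comparison more than the defect does, in the opposite direction.

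**The case against.** **A culture schedule exists.** A reader might infer that no set of cultures is fixed at all. Section 3.7 shows otherwise. What is missing is the link from 7.4 and 7.5 to that schedule, and an end to the window. Nor is a child who leaves partway through day 3 analysable, since three days must be completed; the core day-3 assessment is due in every evaluable child.

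**Missing data belong in an analysis plan.** The protocol nowhere states that an absent culture is scored negative, and an analysis plan not seen here might handle it. This stands in part. But the outcome definition and the evaluability rule are fixed in the protocol. Read together and literally, they let a child with one negative occasion count the same as a child with four.

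**Other analyses help.** The Data Analysis section already plans day-by-day culture positivity and a log-rank analysis of positive stool culture, which can accommodate unequal observation. This stands, but these support the primary success rate and do not define it.

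**Differential loss is unproven.** Both arms follow the same double-dummy schedule, five days in hospital are planned, and attendants are to bring children back. A reader might infer that the comparison is biased toward azithromycin. The documents do not support that: they give no rate of early leaving in either arm, and the 15-point imbalance is purely illustrative. Blinding does not, however, prevent departure that follows the child's clinical course.

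**Conclusion.** The point holds as a defect in the definition of a primary outcome. The culture schedule is sound, but success is not tied to it and has no closing date, so evaluable children are assessed on one to four occasions after 48 hours. For any one child the direction is certain: a missed culture can only favour success. Bias between arms is conditional on differential early departure or missed follow-up, and equal loss dilutes a true late difference.

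The size is unknown. At 5% per later culture and a 15-point imbalance it is at most about 2 points (0.9 to 4.1 over 2 to 10%), and about 0.75 points if only follow-up is missed. The per-culture rates, independence and the imbalance are assumptions. The only margin in the protocol, 10 points, was set for clinical success, so these figures do not show that a conclusion would change. This is a cheap improvement that should be made, not a flaw that invalidates the comparison.

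**What to change.** 1. Redefine primary bacteriological success in 7.4 on a closed window: no isolation of the admission strain in the scheduled cultures of study days 3 to 5. Align 7.5 and the project summary with it.
2. Report isolation at follow-up as relapse, with the children actually cultured there as denominator. This also stops one follow-up isolate from counting both as primary failure under 7.5 and as relapse under 7.6.
3. For evaluable children lacking a day 4 or day 5 culture, do not score success by default. Report the result with them as non-success alongside the day-3 result, and give the number of missing cultures by arm.
4. Reconcile the 7-day and ten-day follow-up.

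**Cost.** Changes of wording and an added tabulation; no new specimens and no change to the sample size. The stated success rate may fall. The missing-as-non-success version can itself be biased if early leaving differs by arm (Step 5), so neither result should be shown without the other.

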1.3 Comparison of the secondary outcome measures

- Rates of clinical and bacteriologic relapse.
- Duration of diarrhoea in hours, and duration of fecal excretion of *V. cholerae* O1 or O139 in days.
- Volume of watery/liquid stool for each 6 and 24 hour of the study, and also the total amount of watery/liquid stools during the study period.
- Frequency of vomiting and the amount of vomitus, and proportion of patients with vomiting on each study day.
- Intake of oral and intravenous fluids for each 24 hour as well as the entire duration of the study.
- Proportion of patients with resolution of diarrhoea on each study day.
- Proportion of patients with a positive culture for infecting *V. cholerae* O1 or O139 on each study day.

2. Statistical methods

Data will be entered onto computer using SPSS for Windows (Version 6.0). Range check and double-entry system will be employed to facilitate data editing and cleaning. The significance of differences in continuous variables will be assessed by Student's t test for data that are normally distributed, or by Mann-Whitney U test for data which are not normally distributed. Significance of differences in the proportions will be assessed by the chi-square test, and Fisher's exact test will be employed when the expected number in any cell in the comparison is 5 or less. Survival analysis (Log Rank Test) will be done for the duration variables such as the proportions of patients with diarrhea, and a positive stool culture for *V. cholerae* O1 or O139 on each day of the study.

Ethical Assurance for Protection of Human Rights

Describe in the space provided the justifications for conducting this research in human subjects. If the study needs observations on sick individuals, provide sufficient reasons for using them. Indicate how subject's rights are protected and if there is any benefit or risk to each subject of the study.

Justifications for conducting this research in human subjects

This objective of this study is to compare clinical and bacteriologic efficacy as well as adverse events in association with therapy for children with clinically severe cholera with a single dose of azithromycin oral suspension with a 3-day course of erythromycin. Both of the study drugs are registered with the Drug Administration, Peoples' Republic of Bangladesh for use in the country.

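### Definition 7.8 gives a completed duration of diarrhoea to a child still passing watery stool when observation ends; the time should be censored

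*Protocol*

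**What the plan says.** Section 7 of the protocol defines duration of diarrhoea (7.8) as "The interval between administration of study drugs to the end of the last 6-hour period the patient had a watery stool". Section 4.2 lists it first among the secondary outcomes, and Data Analysis 1.3 compares "Duration of diarrhoea in hours".

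Four other places decide what that definition produces:

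- Section 3.7, on measuring stool: "This will be done for the rehydration and the observation periods, and for each 6 hour period of hospitalization". Nothing is measured after discharge.
- Section 3.7, on the planned stay: "Study patients will be hospitalized for full five days beginning from the time of initiation of study drug therapy". That is 120 h.
- The project summary, on who is analysed: children with a positive culture "who stay in-hospital for three or more days will be eligible for analysis". Observation may therefore end at 72 h for an analysable child.
- Section 7, definition 7.2, makes clinical failure "Continuation of watery stool for > 96 hours", so the protocol itself foresees children purging late in the stay.

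On tests, Data Analysis 2 says "The significance of differences in continuous variables will be assessed by Student's t test" when the data are normal, with Mann-Whitney otherwise. It also plans a log-rank test for duration variables. Neither that section nor 7.8 says which children are censored.

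**The concern.** The end of the last watery period is a true end of diarrhoea only if the child is later observed without watery stool. Definition 7.8 does not require this. Read literally:

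- Child X purges in every period to 72 h and goes home: duration 72 h.
- Child Y purges to 90 h and is then seen without watery stool: duration 90 h.
- Child Z purges in every period to 120 h: duration 120 h.

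X was never seen to stop, yet ranks ahead of Y, who was. Z receives the value of a child who finished at 120 h. For X and Z the only known fact is that diarrhoea lasted at least that long. A t or Mann-Whitney test takes these values as exact. A log-rank test can handle them properly, but only if they are marked as censored, and no text does so. At stake is the hours comparison for this secondary outcome, in a trial whose hypothesis is that one dose is as effective as the 12-dose course.

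**Working it through.** **Inputs from the protocol.** Clinical success 95% by 96 h, margin 0.10, 58 evaluable children per arm (section 3.6); 6-hour periods and a 120 h stay (section 3.7); 72 h minimum stay (project summary). The protocol gives no figure for duration itself, so only the sample size can be reproduced:

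n = 2P(1−P)(Zα+Zβ)²/d² = 2 × 0.95 × 0.05 × (1.645 + 0.842)²/0.10² = 58.7 per arm, against 58 stated.

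**Assumptions.** Duration shapes (exponential; Weibull with shape 1.5; log-normal), a slower arm with 85% resolved by 96 h (worse by the margin), and all leaving rates.

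**Step 1: everyone observed to 120 h, mean hours.** For the exponential shape the mean is m = 96/(−ln(1−p)), and the mean of the values 7.8 records is m(1−e^(−120/m)).

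- 95% arm: m = 96/2.996 = 32.0 h; recorded 32.0 × (1−0.0236) = 31.3 h. Still purging at 120 h: 58 × 0.0236 = 1.4 children.
- 85% arm: m = 96/1.897 = 50.6 h; recorded 50.6 × (1−0.0933) = 45.9 h. Still purging at 120 h: 58 × 0.0933 = 5.4 children.
- Difference: 18.6 h falls to 14.6 h, about 21% smaller. Simulation with 6-hour rounding gave 14.5 h, about 22% smaller.

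With the Weibull shape the full means are 41.7 and 56.6 h and the recorded means 41.4 and 54.6 h. The difference falls from 14.8 to 13.2 h, about 11% smaller, with 0.9 and 4.1 children of 58 unresolved at 120 h. If both arms resolve 95% by 96 h, the recorded means are equal and no difference is hidden.

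**Step 2: everyone observed to 120 h, tests.** Share of 2,000 simulated trials (58 per arm, 95% v 85%) significant at 5%:

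| Test | Exponential | Log-normal |
|---|---|---|
| t, true durations → 7.8 values | 0.680 → 0.650 | 0.852 → 0.874 |
| Mann-Whitney, true → 7.8 | 0.568 → 0.567 | 0.880 → 0.880 |
| Log-rank, all events v censored | 0.664 v 0.668 | 0.838 v 0.838 |

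The rank-based results are stable for a structural reason. Children unresolved at a common 120 h already hold the top ranks. If everyone still at risk is an event at the last time, observed equals expected there and the log-rank statistic gains nothing.

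**Step 3: leaving early while still purging.** Here 27% of an arm leave at times spread over 72 to 114 h (exponential, 95% v 85%). The 27% is a generous illustration: it is the whole planned loss from 160 to 116 (44/160 = 27.5%), which also covers negative cultures and children who leave too soon to be analysed.

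| Who leaves | Log-rank, all events | Log-rank, censored |
|---|---|---|
| Both arms | 0.622 | 0.643 |
| Slower arm only | 0.611 | 0.672 |
| Faster arm only | 0.704 | 0.663 |

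Scoring leavers as finished hides a difference when the slower arm leaves more and exaggerates it when the faster arm does. With both arms at 95% and 27% leaving from one arm only, the rejection rate stayed near 5% (0.050 v 0.052).

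**Step 4: how many children.** At 95% success, 6.1 (exponential) to 8.3 (Weibull) of 58 would still be purging at 72 h. If 27% left at exactly 72 h, 0.27 × 6.1 = 1.6 to 0.27 × 8.3 = 2.2 children per arm would leave purging.

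**The case against.** The strongest reply is that the plan already contains the right tool. A log-rank test is planned for duration variables, event coding is often left to a statistical analysis plan, and the use of t or Mann-Whitney on this outcome is inferred from a general sentence about continuous variables. In part this stands: the log-rank test is the right vehicle. But 7.8 is not silent. It fixes an end time for every child with no status attached, and Data Analysis 1.3 compares that time in hours, so anyone applying the text as written gets the wrong value for X and Z.

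Second, a reader might infer that the rule always makes the arms look more alike and so favours the hoped-for conclusion. The documents do not support that. With a common 120 h end only the mean difference shrinks, and the rank-based tests do not move. Even the t test moves down under one assumed shape and up under another. With early leaving, the direction depends on the arm.

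Third, a reader might infer that a child purging at 120 h is counted as cured. That is not so: the child is a clinical failure under 7.2, and the primary clinical success rate rests on 7.1, not 7.8.

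Fourth, the untruncated mean is a doubtful benchmark. Section 3.8 gives clinical failures another antimicrobial, so later hours no longer reflect study drug alone. This objection stands: the 11 to 22% measures truncation and is not an effect the trial could have observed.

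Finally, section 3.7 plans five full days for everyone, and the documents give no rate of leaving between 72 and 120 h.

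**Conclusion.** The point holds in a limited form. As worded, 7.8 records a completed and too short duration for a child with watery stool at the end of observation, and it can rank a child who left unresolved ahead of one who was seen to recover. The planned log-rank test does not cure this, because no censoring status is assigned.

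With all children observed to 120 h, the cost is an understated difference in mean hours, about 11 to 22% at 95% v 85%, with Mann-Whitney and log-rank almost unchanged. Early leaving while purging is the case that can alter the comparison, in either direction. Even at a generous 27% leaving, the log-rank rejection rate moved by 0.02 to 0.06. Concentrating the leaving at 72 h makes the one-sided cases worse.

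All of this rests on assumed shapes, an assumed slower arm and assumed leaving rates. At the protocol's 95% success rate only one or two children per arm are involved. The outcome is secondary and the primary clinical comparison is untouched. The change is worth making because it is nearly free and corrects a value that the rule gets wrong.

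**What to change.** Add to 7.8: *If watery stool was present in the last 6-hour period observed, the duration is censored at the end of that period.*

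In Data Analysis 2, name the log-rank test on 6-hour times with this censoring, together with Kaplan-Meier medians, as the comparison for duration of diarrhoea. It then takes the place of a t or Mann-Whitney test on the 7.8 values for this outcome. Report by arm how many children were censored before 120 h, since censoring assumes that leaving is unrelated to how long the diarrhoea would have lasted.

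The cost is two sentences. No new data are needed: the 6-hourly stool record already shows whether the last period was watery, and the test is already planned. The downside is that a median is reported in place of a mean.
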